#### *Predictive Gene Expression Signature*

In order to investigate gene expression signatures that could predict arm stratification, we divided our patients into two cohorts and performed principal component analysis (PCA) for dimensionality reduction (see workflow in **Figure 2a**). We used Limma for supervised feature selection between cohorts, which identified 231 differentially expressed genes (DEGs). We then applied a neural network to the 231 DEG expression matrix to compute a classification score. The ROC curve of the resulting classifiers is presented in **Figure 2b**. The resulting area under the receiver operating characteristic (AUC) is 0.92. This estimate of the AUC, being based on the training set, is optimistically biased and we do not anticipate a validated AUC this close to 1, but it demonstrates the feasibility of the approach. Developing a clinically actionable predictive model requires a larger training set and an independent validation set from the ECOG 3311 cohort.

Figure 2

*Ongoing work*

The predictive signature discussed above employs only gene expression data. However, numerous genomic features may be important in predicting arm stratification. Thus, we are currently employing more advanced and comprehensive modeling to generating predictive signatures which include more varied data input including from both DNA and RNA (**Figure 3**). These more comprehensive approaches will help refine and improve the accuracy of our predictive signature.

Figure 3

Funding for the project will come from Hillman Cancer Center funds, and R01 submission in progress (depends on a support letter from ECOG providing and ensuring access to the national specimens, beyond the UPMC -enrolled patients which comprise the preliminary data).

**3) Biospecimen Requirements**

**Tissue (slides, cores, etc.):** 10 tumor blanks (or 1 3-4mm core) or if pre-processed 300ng DNA (>20ul and >10ng/ul) and 1ug total RNA (>20ul and >10ng/ul)

**Blood (tube type, volume, etc.):** 5ml of blood or if pre-processed 300ng DNA (>20ul and >10ng/ul). Blood can come from any time collection point

---

**1 of each sample type is to be requested per case.**

266 cases in the trial currently have these sample types available and all 266 will have these samples requested. This analysis will not exhaust any cases of material.

**4) Sample Processing/Laboratory Methods**

*Tissue*

Microdissection of FFPE primary tumor from 10 FFPE slides at 5 microns will be performed manually using an inverted microscope (Nikon Eclipse TE200) to obtain a minimum of 95% tumor cells avoiding domains with infiltrating inflammatory cells, necrotic tissue or normal cells. Dissection involves scraping tumor cells from unstained sections of 5 micron thickness on slides aligned in register with serially cut hematoxylin and eosin stained specimens including tumor domains demarcated by consensus analysis of two surgical pathologists or as provided by ECOG

*Whole Exome Sequencing (WES)*

DNA extraction and QC: Genomic DNA will be purified from tumors using the Qiagen QIAamp FFPE DNA protocol (Qiagen, Valencia, CA). DNA concentration and quality will be determined by fluorometry and spectrophotometry respectively (Qubit 2.0 fluorometer, Thermo Fisher, Waltham, MA; Nanodrop ND-1000 spectrophotometer, NanoDrop, Wilmington, DE) and molecular size distribution (20Kb to 150Kb) is evaluated on the Bioanalyzer 2100 (12000 DNA Chip, Agilent Technologies, Santa Clara, CA). Samples that do not meet the minimum picogreen quantified input requirements ( $\geq 300$ ng DNA, preferred concentration 10ng/ul, or a minimum Kapa quality score of  $> 0.3$ ) will be held for further evaluation.

Library construction: Library construction will be performed at the Broad Institute according to established protocols with the ligation-based KAPA HyperPrep Library Preparation Kit followed by hybrid capture with the Rapid Capture Exome enrichment kit (Illumina) with 38Mb target territory. All samples will be validated against the Fluidigm Fingerprint Check to confirm sample identity and fidelity. One positive control, NA12878 is included in each library preparation.

Sequence generation: All libraries will be sequenced to 85% of targets covered at greater than 50x coverage ( $\pm 5\%$ ) ( $\sim 150$ X MTC) for tumor samples, and 80% of targets covered at greater than 20x coverage ( $\pm 5\%$ ) for matched-normal samples utilizing the Laboratory Picard bioinformatics pipeline. All sequencing will be performed on the Illumina HiSeq instruments with 76 base pair, paired-end sequencing. The Picard pipeline will aggregate all data from a particular sample into a single BAM file which will include all reads, all bases from all reads, and original/vendor-assigned quality scores.

Somatic variant calls and copy number variants (CNV): GATK best practices core variant calling workflow including pre-processing and Variant Discovery will be used. Pre-processing includes mapping (BWA mem) and duplicate marking for individual sequencing output. Local indel realignment is subsequently performed jointly on the tumor normal pair, prior base quality score recalibration (BQSR), and contrastive evaluation between the tumor and normal using Mutect and Indelocator in order to provide somatic SNV and Indel calls. These variants are further annotated and visualized using maftools.

*Whole Transcriptome Sequencing (WTS)*

RNA extraction and QC: Specimens with projected yield  $> 1$   $\mu$ g RNA will be extracted with the Qiagen FFPE RNeasy kit (#73504, Qiagen, Inc., Venlo, Netherlands) while specimens with

projected yields less than that utilize the Zymo RNA FFPE extraction kit (#R1008, Zymo Research, Irvine, CA). Total RNA purity will be measured by the absorbance ratio (260nm/280nm) in Tris buffer (10mM TRIS-Cl, pH 7.5) using the Nanodrop 1000 spectrophotometer (ThermoFisher, Wilmington, DE) with a pure RNA A260/280 of 2.0 and low cutoff of 1.8. Samples  $\geq 1.8$  undergo further processing. The concentration of RNA ( $> 20$  nucleotides) is determined on the Qubit fluorometer (ThermoFisher) High Sensitivity assay on RNA diluted to 50ng/ $\mu$ l using the Nanodrop concentration. The micro-RNA Qubit assay will then be used to quantitate RNA that is present  $< 20$  nucleotides length. Agilent Bioanalyzer 2100 (Agilent Technologies, Santa Clara, CA) will be used to determine the RNA size profile (RNA Integrity Index: RIN) and the DV200% of the eluted RNA using the RNA Nano chip assay ( $> 50$  ng) or the Pico chip for RNA samples with less than 50 ng. Samples that do not meet the minimum quantified input requirements ( $\geq 550$ ng RNA, preferred concentration 10ng/ $\mu$ l, DV200 score  $> 0.3$ ) will be held for further evaluation.

Library construction: Library construction will be performed at the Broad Institute according to established protocols with the True-Seq RNA Exome Kit (Illumina). All samples will be validated against the Fluidigm Fingerprint Check to confirm sample identity and fidelity.

Sequence generation: All libraries will be sequenced to 50M reads aligned in pairs ( $\pm 5\%$ ) at 76bp read length using the Illumina HiSeq platform as measured using the Picard bioinformatics pipeline. The Picard pipeline aggregates all data from a particular sample into a single de-multiplexed, aligned BAM file which includes all reads, all bases from all reads and original/vendor assigned quality scores.

Read counts: Quality checked and adapter trimmed fastq reads will be mapped to the reference genome using HISAT2 aligner and gene level quantitation performed using HT-Seq counts. Count data are used to perform differential gene expression between two conditions using edgeR, a bioconductor R package.

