#### *Informatics for Objective 1.*

The predictive model will be developed as follows based on the sequencing from 200 samples (100 samples from UPMC and 100 samples from Arms A+B+C of ECOG 3311). For RNA-seq data, the gene level, transcript level, and exon level expression profiles will be extracted and submitted to unsupervised PCA analysis, to observe the PCA clusters that can facilitate stratification. In addition, we will use TopHat2 and MapSplice2, together with the fusion zoom pipeline we developed, to detect splice junctions and gene fusions from RNAseq data, and use MuTect2 and GATK4 to detect somatic mutations, such as SNVs and indels, and CNVs from WXS data, which can be used as additional levels of genomic features for stratification. The individual discriminative features for arm stratification will be selected and Autoencoder will be applied to transform these discriminative features into synthetic features for dimensionality reduction. We will then classify tumor samples based on these synthetic features using Neural Network, Ridge, Lasso, and Elastic Net, selecting the method with the best cross-validated predictive performance. In addition to these machine learning methods, we will also apply a Universal Genomic Signature Analysis (uniGenSig), developed in our laboratory, to explore the universal genomic correlates that can be deployed for stratification. This method does not require dimensionality reduction, but instead extracts the universal genomic correlates via feature selection and then eliminates their redundancy by assessing their co-occurrence in large cohorts of human tumors. Together, these comprehensive genomic analyses will characterize the individual, synthetic, and universal genomic correlates for stratification.

---

*Informatics for Secondary Objectives in 1.*

1. Generate genomic and transcriptomic profile of all tumors from ECOG 3311. From DNA, SNVs, indels and CNVs for each sample will be annotated and collated. From RNA, as well as gene expression and gene fusions will be generated. Profiles will be compared against existing HPV+ samples from TCGA. This data will be available to the scientific community as a reference for investigation.
2. Test if TRAF3/CYLD mutation presence predicts arm stratification: Somatic alterations, including CNVs in TRAF3 and CYLD will be annotated for each tumor and grouped by arm to examine differences between arm D and others.

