3. Neoantigen prediction requires three components: somatic variant calls, expression levels of mutant genes and HLA genotyping. Somatic variant calls and gene expression will be generated as part of the primary objective, HLA genotyping will be performed using the BWAKit and Polysolver algorithms from the WES data. Neoantigen prediction will then be performed according to the methods described by Rooney[12]. Number of neoantigens will then be pooled and averaged across study arms and compared between arms.
4. Test if APOBEC mutational burden predicts arm stratification: APOBEC mutational burden will be calculated for each sample using established functions[13], pooled and averaged by study arm, and compared between arms.
5. Test if an inflamed expression profile predicts arm stratification: Keck and Seiwert have defined an inflamed expression profile for a subset of HPV+ HNSCCs[14]. We will apply this inflamed vs classical expression profile to all samples and test if expression subtype predicts arm stratification according.
6. Test if CYT score and T-cell infiltrate predicts with arm stratification. Rooney et defined an immune cytolytic activity score (CYT) based on transcript levels of granzyme A and perforin[12]. Using RNA-Seq data will we calculate CYT scores for each sample and correlate this with arm stratification. Senbabaoglu et al defined methods for establishing T-cell infiltration scores using RNA-Seq data via ssGSEA[15]. Mandal et al later applied these methods to HNSCC[16]. We will calculate T-cell infiltration scores using ssGSEA methodology as defined by Senbabaoglu for each sample. Scores will then be correlated with arm stratification.
7. Clinical outcome and progression-free survival will also be modeled in a fashion similar to that of the primary informatics objective, but this is considered exploratory and will not be submitted to validation.

Nucleic acid extraction will be performed at the UPMC Hillman Genomics Core. Over the last 2 years, this group has extracted DNA and RNA from >200 FFPE samples that have gone on to NGS with success, including the 40 FFPE patient samples from patients at University of Pittsburgh. [name] will oversee this process.

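### Appendix X microdissects slides to at least 95% tumour cells and avoids inflamed areas, so item 6's cytolytic and T-cell scores from that RNA cannot be reported as tumour immune infiltrate

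*Combined protocol and SAP*

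**What the plan says.** The point lies within Appendix X (the E3311LGS1 laboratory substudy).

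- **Tissue handling.** Section 4, under Tissue, ahead of both the exome and the transcriptome methods: "Microdissection of FFPE primary tumor from 10 FFPE slides at 5 microns will be performed manually", with the aim "to obtain a minimum of 95% tumor cells avoiding domains with infiltrating inflammatory cells, necrotic tissue or normal cells". Tumour areas are marked by two surgical pathologists in consensus, or as supplied by ECOG.
- **RNA.** The transcriptome paragraph, beginning "RNA extraction and QC: Specimens with projected yield", describes extraction from the specimens. It mentions no whole-section or undissected aliquot. Samples below 550 ng RNA are held for further evaluation.
- **Sample formats.** Section 3 asks for 10 tumour blanks, or one 3-4 mm core, or pre-processed DNA (300 ng) and RNA (1 µg). Microdissection is described for slides only.
- **Immune analyses.** These stand under "Informatics for Secondary Objectives in 1". Item 5: "Test if an inflamed expression profile predicts arm stratification", with the commitment "We will apply this inflamed vs classical expression profile to all samples and test if expression subtype predicts arm stratification". Item 6: "Test if CYT score and T-cell infiltrate predicts with arm stratification". It uses a published method that "defined an immune cytolytic activity score (CYT) based on transcript levels of granzyme A and perforin", and adds ssGSEA T-cell infiltration scores. Both are calculated for each sample from the RNA-Seq data.
- **Source of cases.** Section 5: the training set is 100 cases from E3311 Arms A+B+C and 100 Arm D-like cases from the University of Pittsburgh. The validation set is 70 cases from Arms A+B+C and 70 from Arm D, all from E3311.

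**The concern.** One step in the laboratory plan selects against inflammatory cells; a later step sets out to quantify them in the same material. Granzyme A, perforin and T-cell signatures are used in item 6 as readouts of immune infiltrate. If the areas where that infiltrate is concentrated are left on the slide, the scores describe what remains among the tumour cells, not the tumour's infiltrate.

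What is at stake is how the result is read. A null association with arm could be reported as evidence that infiltrate does not distinguish Arm D patients, when the handling had already taken out much of the variation. A positive association could partly reflect how thoroughly different slides were dissected, or which format or source a sample came from. The plan offers no purity adjustment and no undissected comparator, and it does not acknowledge the conflict.

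**Working it through.** The plan gives no figure for this point, so there is none to reproduce. The check sets the methods side by side and then bounds the loss.

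**Step 1: does the same RNA feed both?** For slides, yes. The dissection is described once, before both assays. The RNA paragraph adds no second stream, and item 6 names the RNA-Seq data as its input for each sample.

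**Step 2: what does the purity rule imply?** Tumour cells make up at least 0.95 of the dissected sample. All other cells together, immune cells included, are therefore at most 1 − 0.95 = 0.05.

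**Step 3: how much immune content is lost?** Let f be the immune fraction in undissected tissue. The documents do not give f, so the values below are assumptions. If the purity target is met:

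minimum proportional loss = 1 − 0.05/f

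| Assumed f | Calculation | Minimum loss |
|---|---|---|
| 10% | 1 − 0.05/0.10 | 50% |
| 20% | 1 − 0.05/0.20 | 75% |
| 30% | 1 − 0.05/0.30 | 83% |
| 40% | 1 − 0.05/0.40 | 88% |

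At f = 5% or below the rule by itself guarantees no loss.

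**Step 4: what happens to the spread between patients?** A quantity confined to 0-5% has a standard deviation of at most (5 − 0)/2 = 2.5 percentage points. If native fractions ran from 10% to 40% (assumed), the range would fall from 30 points to at most 5, that is 30/5 = at least 6-fold. If they ran from 5% to 15% (assumed), it would fall from 10 points to at most 5, at least 2-fold. The factor depends wholly on the assumed range.

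**Step 5: are samples comparable with each other?** A core or pre-processed RNA carries no described dissection, so the 5% cap need not apply to it. Pooling such samples with dissected ones mixes two scales. In the training set, source coincides with arm group (Pittsburgh for the Arm D-like cases, E3311 for Arms A+B+C), and the marking of tumour areas may come from either of two routes. If format or marking differs by source, residual immune content would differ by arm group for reasons unrelated to biology. The validation set, all from E3311, does not have this alignment by source.

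**Step 6: does item 5 follow?** Only in part. Appendix X names genes for the cytolytic score but takes the inflamed profile from a cited paper without listing its genes. An immune component is likely from the name, but the documents do not confirm it.

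**The case against.** The strongest reply has four parts.

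- **Some immune signal survives.** The rule avoids areas with inflammatory cells and tolerates up to 5% non-tumour cells, so lymphocytes scattered within tumour nests may remain. This stands. A reader might infer that dissection removes the immune signal altogether, or that what is left measures only dissection technique. The documents support neither: they support depletion and truncation, and say nothing on whether the residual variation is noise or biology within the nests.
- **Not all RNA need be dissected.** A reader might infer that every sample is. Section 3 also accepts cores and pre-processed RNA, so that is not established. This does not rescue item 6, because mixed formats add a comparability problem.
- **Compression alone need not destroy an association.** The 5% cap concerns cells, whereas the scores use transcripts, and ssGSEA works on ranks. If dissection kept patients in the same order, a rank comparison with arm would be unchanged. This is correct, and it is why no bias or power loss is claimed here. But nothing in the plan shows that order is preserved.
- **These are secondary laboratory analyses.** They carry no alpha, power or treatment decision, and high tumour purity suits exome variant and copy-number calling. Both are true, and they limit the weight of the point. Section 12.2.7 of the main protocol does mention profiling tumour-infiltrating lymphocytes, but only as something to be considered, not as the source of these scores.

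**Conclusion.** For slide-derived samples the conflict is real and item 6 is wrong as written: it would report as tumour immune infiltrate a quantity that the handling depletes and caps. Item 5 is probably affected, to a degree the documents do not let one settle. The cap of 5% is firm if the purity target is met. The losses of at least 50% to 88% rest on assumed native fractions of 10% to 40%, and the true size is unknown. Possible non-comparability across formats, and the alignment of source with arm group in training, are further reasons not to take the scores at face value.

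A reader might go further and infer that the primary AUC validation fails. The documents do not support that. The classifier also uses expression data and may lose immune-related signal, but Section 5 has the validation samples assayed in a similar fashion to the training set, and the AUC test concerns the classifier so built. The point is confined to what items 5 and 6 can conclude.

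**What to change.** In the secondary-objectives text of Appendix X:

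1. Do not interpret item 6, or item 5 where its genes are immune-derived, as tumour immune infiltrate when the RNA was microdissected. Relabel the scores as tumour-compartment expression and state that a null result does not show infiltrate to be unrelated to arm. Otherwise drop the items.
2. Record sample format (dissected slide, core, pre-processed nucleic acid) and source for each case. Do not pool dissected with undissected samples without accounting for it.

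The cost is a text change, two recorded fields and a narrower secondary claim.

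If the infiltrate question matters to the substudy team, two additions are optional:

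- **Score infiltrate on the existing H&E sections.** This needs reading time, preferably from the same readers for all cases, since the existing marking covers tumour areas only. It does not give a granzyme/perforin score and does not address item 5.
- **Take RNA from undissected tissue.** This serves both items but needs a second library and enough yield. If the 10 blanks are treated as equivalent to the 1 µg RNA alternative (an assumption), one slide gives about 1,000/10 = 100 ng against the 550 ng threshold, so a single slide would probably not suffice. Section 3 says the analysis will not exhaust any case, so further sections may be available.

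Either addition that needs tissue should be decided before slides are scraped, because dissected sections cannot be recovered.

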#### *Informatics for Objective 1.*

The predictive model will be developed as follows based on the sequencing from 200 samples (100 samples from UPMC and 100 samples from Arms A+B+C of ECOG 3311). For RNA-seq data, the gene level, transcript level, and exon level expression profiles will be extracted and submitted to unsupervised PCA analysis, to observe the PCA clusters that can facilitate stratification. In addition, we will use TopHat2 and MapSplice2, together with the fusion zoom pipeline we developed, to detect splice junctions and gene fusions from RNAseq data, and use MuTect2 and GATK4 to detect somatic mutations, such as SNVs and indels, and CNVs from WXS data, which can be used as additional levels of genomic features for stratification. The individual discriminative features for arm stratification will be selected and Autoencoder will be applied to transform these discriminative features into synthetic features for dimensionality reduction. We will then classify tumor samples based on these synthetic features using Neural Network, Ridge, Lasso, and Elastic Net, selecting the method with the best cross-validated predictive performance. In addition to these machine learning methods, we will also apply a Universal Genomic Signature Analysis (uniGenSig), developed in our laboratory, to explore the universal genomic correlates that can be deployed for stratification. This method does not require dimensionality reduction, but instead extracts the universal genomic correlates via feature selection and then eliminates their redundancy by assessing their co-occurrence in large cohorts of human tumors. Together, these comprehensive genomic analyses will characterize the individual, synthetic, and universal genomic correlates for stratification.

---

*Informatics for Secondary Objectives in 1.*

1. Generate genomic and transcriptomic profile of all tumors from ECOG 3311. From DNA, SNVs, indels and CNVs for each sample will be annotated and collated. From RNA, as well as gene expression and gene fusions will be generated. Profiles will be compared against existing HPV+ samples from TCGA. This data will be available to the scientific community as a reference for investigation.
2. Test if TRAF3/CYLD mutation presence predicts arm stratification: Somatic alterations, including CNVs in TRAF3 and CYLD will be annotated for each tumor and grouped by arm to examine differences between arm D and others.
3. Neoantigen prediction requires three components: somatic variant calls, expression levels of mutant genes and HLA genotyping. Somatic variant calls and gene expression will be generated as part of the primary objective, HLA genotyping will be performed using the BWAKit and Polysolver algorithms from the WES data. Neoantigen prediction will then be performed according to the methods described by Rooney[12]. Number of neoantigens will then be pooled and averaged across study arms and compared between arms.
4. Test if APOBEC mutational burden predicts arm stratification: APOBEC mutational burden will be calculated for each sample using established functions[13], pooled and averaged by study arm, and compared between arms.
5. Test if an inflamed expression profile predicts arm stratification: Keck and Seiwert have defined an inflamed expression profile for a subset of HPV+ HNSCCs[14]. We will apply this inflamed vs classical expression profile to all samples and test if expression subtype predicts arm stratification according.
6. Test if CYT score and T-cell infiltrate predicts with arm stratification. Rooney et defined an immune cytolytic activity score (CYT) based on transcript levels of granzyme A and perforin[12]. Using RNA-Seq data will we calculate CYT scores for each sample and correlate this with arm stratification. Senbabaoglu et al defined methods for establishing T-cell infiltration scores using RNA-Seq data via ssGSEA[15]. Mandal et al later applied these methods to HNSCC[16]. We will calculate T-cell infiltration scores using ssGSEA methodology as defined by Senbabaoglu for each sample. Scores will then be correlated with arm stratification.
7. Clinical outcome and progression-free survival will also be modeled in a fashion similar to that of the primary informatics objective, but this is considered exploratory and will not be submitted to validation.

Nucleic acid extraction will be performed at the UPMC Hillman Genomics Core. Over the last 2 years, this group has extracted DNA and RNA from >200 FFPE samples that have gone on to NGS with success, including the 40 FFPE patient samples from patients at University of Pittsburgh. [name] will oversee this process.

QC, library preparation and sequencing will be performed at the Broad Institute of MIT and Harvard in collaboration with [name] (MEEI/MGH/HMS). [name] will oversee this process. Broad Genomics has a 25-year track record of leading the field of genomics (Human Genome Project, 1000 Genomes Project, The Cancer Genome Atlas, etc.) and is the largest producer of human genomic information in the world, producing genomic data at a rate of one 30X human whole genome every 12 minutes. The group has processed more than 1.5 million samples from more than 1400 groups in over 50 countries. Their success is well published.

